6.1 Schedule of procedures

6.1.1 Visit 1 (Screening visit)

Prospective, eligible participants with documented systolic heart failure meeting study inclusion criteria will undergo a screening visit.

The following procedures will be performed at the screening visit:

- Demographic information, medical history (including NYHA class and most recent creatinine value), physical examination, current medical treatments
- Minnesota Living with Heart Failure quality of life (MNQOL) score
- Fasting blood draw: ONE 5mL pearl top tube (for BNP), TWO 3mL lavender top tubes (for CBC, HbA1C); ONE 4mL lime top tube [for uric acid, ALT, CK, Chemistry panel (electrolytes, glucose, blood urea nitrogen and creatinine)], ONE 4mL gold SST tube (for insulin) ONE 2.7 mL “blue top” tube for whole blood NR and NAD+ levels and FOUR 4.5 mL GLASS blue top tubes (for mitochondrial function)
- Urine pregnancy test at screening in women of child-bearing age
- Six-minute walk test (6MWT)
- Dispense placebo to take twice daily

6.1.2 Visit 2 (Randomization visit)

After successful completion of the Screening visit, the participant will return for the Baseline Visit, at which participants would be randomized in a 2:1 allocation to receive blinded study medication with nicotinamide riboside or matching placebo. All participants who are randomized are irrevocably in the study, whether or not they are subsequently found to be eligible or actually receive the allocated treatment, and they should be followed until the study end date or death. Study drug administration should be initiated as soon as possible after treatment allocation.

The following procedures will be performed at the randomization visit:

- Update as needed demographic information, medical history, current medical treatments
- Vital signs and weight
- Randomization by investigational drug services.
- BASELINE MNQOL score
- BASELINE 6MWT
- BASELINE echocardiography (TTE and TDI) This may also take place at screening if needed due to scheduling
- Dispense blinded study medication:
 - 250mg PO BID or Placebo for one week
 - 500mg PO BID or Placebo for one week

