**NR in HF Study: Biostatistical Analysis Plan.**

**5.a. Statistical Methods.** After import into statistical software (R, Stata or SAS), data will be screened for outliers and the validity of any outlier values will be verified and/or any potential errors will be corrected. Changes in outcomes (including serum NR level, NADH/NAD+ ratio, 6MWT, MNQOL score, 3D-Echo, Doppler/TDI) from Week 0 to Week 12 will be compared between the NR and placebo arms using a two-sample t-test, the Mann-Whitney test or the permutation test, as appropriate. Changes in serum NR, NADH/NAD+ levels, 6MWT and MNQOL score outcomes over the multiple visits (0, 2, 4, 6, 8 and 12 Weeks) will be explored visually and by calculating and tabulating mean outcomes for each visit by assigned treatment.

Power calculations. Detectable differences for LVEF are calculated from power calculations for a two-sample t-test (PASS 2008, NCSS, Kaysville, UT), using the initial sample sizes of 20 patients in the NR group, 10 patients in the placebo group, and a dropout rate of 10%, leading to a final expected sample size of 18 and 9 patients in the NR and placebo groups, respectively. Two-sided tests, 0.05 significance level and 80% power are assumed. Based on these parameters we calculate a detectable difference of 1.190 standard deviations for a change in an outcome between the means in the placebo and NR groups. The standard deviation (SD) for the change in LVEF by 3D Echo is based on a study of 50 patients with LV dysfunction due to previous MI (32). The SD for change, measured between baseline and one year follow-up, was 7%, and scatterplots for the LVEF changes measured by MRI or 3D echo suggested that SD values for EF are similar for both modalities. We conservatively assumed that the SD at 12 weeks would not be smaller than that at 52 weeks.

Expected results. Assuming a 7% SD for LVEF change (32), the detectable difference by 3D-TTE for this 30 participant trial is 8.3%. Much larger sample sizes would be required to detect much lesser changes in LVEF. Thus, Study echocardiograms will explore the potential range of effect sizes for NR on LVEF.

|   |   |                   |
|---|---|-------------------|
| 
Table 1. Sample sizes to detect 5% or 3% differences in LVEF at 80%, 85% or 90% power (1:1 randomization and 2-sided <math>\alpha=0.05</math>). Total sample sizes are shown.
 | 
Sample Sizes (N) to Achieve Power of:
 |                   |

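### 6MWT and MNQOL are each measured twice before active drug, but the SAP compares unadjusted change scores and gives the first value no stated role; a baseline-adjusted model would recover precision.

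*Protocol*

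**What the plan says.** Protocol 6.1.1 (Visit 1, screening) lists a six-minute walk test and the "Minnesota Living with Heart Failure quality of life (MNQOL) score", and ends with "Dispense placebo to take twice daily". Protocol 6.1.2 (Visit 2, randomization) repeats both measures as "BASELINE 6MWT" and "BASELINE MNQOL score". Active drug is first dispensed at Visit 2, so each outcome is scheduled twice before any participant takes NR.

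SAP 5.a says that changes in the outcomes, 6MWT and MNQOL among them, "from Week 0 to Week 12 will be compared between the NR and placebo arms using a two-sample t-test", with the Mann-Whitney and permutation tests as alternatives. None of these adjusts for baseline. The SAP also tabulates mean 6MWT and MNQOL at weeks 0, 2, 4, 6, 8 and 12, with no separate entry for screening. It does not define Week 0, and it does not say whether the Visit 1 values are averaged, used as covariates or set aside as familiarisation.

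**The concern.** A raw change score gives the baseline a fixed weight of one. Any visit-to-visit noise in that single reading passes straight into the outcome. A model that adjusts for baseline estimates the weight instead, and a second pre-treatment reading can add information about each participant's underlying level.

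SAP 5.a expects 18 NR and 9 placebo completers, and the comparison can detect only a difference of 1.190 SD of change. Exploring the range of effects on surrogate endpoints is one of the three objectives in Protocol section 2. What is at stake is wider intervals for 6MWT and MNQOL than the collected data require. The validity of the comparison is not in question.

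**Working it through.** **Inputs from the documents.** 18 and 9 completers, two-sided 0.05, 80% power, detectable difference 1.190 SD of change, SD of LVEF change 7% (all SAP, Power calculations). The documents give no correlations, so those below are assumptions.

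**The plan's own figure.** Solving the noncentral t power equation with 25 degrees of freedom and group sizes 18 and 9 gives 1.1901 SD. Then 1.190 × 7% = 8.33%. Both stated figures reproduce.

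**Notation.** Variances are set to 1 at every visit. r1 and r2 are the correlations of the Visit 1 and Visit 2 values with Week 12, and r12 is the correlation between the two baselines.

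- Change from Visit 2: V = 2(1 − r2).
- Change from the mean of both: V = 1 + (1 + r12)/2 − (r1 + r2).
- ANCOVA on Visit 2 alone: V = 1 − r2².
- ANCOVA on both: V = 1 − (r1² + r2² − 2·r1·r2·r12)/(1 − r12²). With r1 = r2 = r this is 1 − 2r²/(1 + r12).

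**Allowance for estimating covariates.** Chance imbalance in k covariates inflates the expected variance of the treatment contrast by (f − 1)/(f − k − 1), where f = 25. This is 24/23 = 1.043 for one covariate and 24/22 = 1.091 for two. A simulation with 18 and 9 participants and two normal covariates gave 1.091.

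**Results for r2 = 0.7.** The change score from Visit 2 has V = 0.60, and the ratios are relative to that.

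| r1 | r12 | ANCOVA, both: V | Ratio | Ratio × 24/22 | Mean-of-two change: V | Ratio |
|---|---|---|---|---|---|---|
| 0.7 | 0.7 | 0.424 | 0.71 | 0.77 | 0.45 | 0.75 |
| 0.7 | 0.8 | 0.456 | 0.76 | 0.83 | 0.50 | 0.83 |
| 0.7 | 0.9 | 0.484 | 0.81 | 0.88 | 0.55 | 0.92 |
| 0.6 | 0.8 | 0.506 | 0.84 | 0.92 | 0.60 | 1.00 |
| 0.6 | 0.9 | 0.505 | 0.84 | 0.92 | 0.65 | 1.08 |

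**On the scale of the detectable difference.** Multiplying 1.190 by the square root of the allowed ratio gives 1.190 × √0.77 = 1.04, 1.190 × √0.88 = 1.12 and 1.190 × √0.92 = 1.14, in units of the original change SD. Using 23 rather than 25 degrees of freedom for the t quantile adds about 0.004.

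**How much is due to the second baseline.** ANCOVA on Visit 2 alone gives (1 − 0.49)/0.60 = 0.85, or 0.85 × 24/23 = 0.89 after allowance. Adding Visit 1 improves this to 0.77 in the first row, barely changes it in the third (0.88), and costs a little in the last two (0.92). Adjustment is the dependable part of the gain. The second covariate helps when the two baselines are noisy and about equally predictive.

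**Other correlations.** With r1 = r2 between 0.5 and 0.8 and r12 from the larger of r and 0.7 up to 0.95, the ANCOVA ratio with both baselines runs from 0.71 to 0.86, or 0.77 to 0.94 after the 24/22 allowance.

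**The case against.** Taking the last value at the end of a placebo run-in as baseline is ordinary practice, and the plan contains no error in doing so. Visit 1 is earlier and precedes the run-in, so it may predict Week 12 less well than Visit 2 does. The first walk may also serve partly as practice. A common practice shift cancels between randomized arms, but differences between participants in practice or placebo response do not. All of this stands. It is the reason not to average, and not to assume equal correlations. It does not defend the raw change score, which gave a larger variance than ANCOVA in every case tabulated. MNQOL is a questionnaire, so the practice-walk argument does not reach it.

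It also stands that these outcomes are exploratory, that no 6MWT or MNQOL target is set, and that the power text concerns LVEF.

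A reader might infer three stronger things that the documents do not support.

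- *That averaging the two baselines is a free gain of 8% to 25% in variance.* Those figures hold only if both baselines correlate equally with Week 12. At 0.6 and 0.7 the gain is zero or a loss of 8%.
- *That the Visit 1 values certainly enter no analysis.* This is an inference from the Visit 2 labels and the SAP's list of weeks. Week 0 is undefined, and for whole-blood NR and NAD+ the only pre-treatment draw listed is at Visit 1, so Week 0 cannot mean Visit 2 for every outcome.
- *That the baselines are taken after allocation, because 6.1.2 lists randomization above them.* That list is unnumbered and states no sequence, dispensing comes last in it, and the study medication is blinded. No bias is shown.

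**Conclusion.** The point holds as a minor loss of precision in two exploratory outcomes. SAP 5.a uses unadjusted change although two pre-treatment readings are scheduled. Adjusting for both gives an expected variance of about 0.77 to 0.88 of the change-score variance if each baseline correlates 0.7 with Week 12 and the two correlate 0.7 to 0.9 with each other. It is about 0.92 if Visit 1 correlates only 0.6. These figures assume equal variances, a linear relation, 27 completers and correlations that the documents do not supply, so the size is indicative. The LVEF figures are untouched: LVEF is scheduled for one baseline echocardiogram, and 1.190 SD and 8.3% remain as stated.

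**What to change.** In SAP 5.a, before unblinding:

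- Compare Week 12 6MWT and MNQOL between arms with a linear model containing treatment and, as covariates, the Visit 1 and Visit 2 values. Report the adjusted difference with its 95% confidence interval.
- Keep Visit 2 as the baseline in descriptive tables and for within-arm change.
- Define Week 0 for each outcome by visit, including blood NR and NAD+.
- If the sponsor regards Visit 1 as familiarisation only, say so and adjust for Visit 2 alone. At a correlation of 0.7 this still gives a ratio of about 0.89.
- Do not make change from the mean of the two baselines the default.

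The cost is SAP wording and two degrees of freedom. No visit, test or participant is added, because both readings are already in the schedule. The rule should also say what is done when one of the two baseline values is missing, so that no participant is lost from the model for that reason.

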6.1.3 Follow-up visit 3 (week 2)

The following procedures will be performed at the follow-up visits (Day 14±3):

- Update as needed demographic information, medical history, current medical treatments
- Vital signs and weight
- MNQOL score
- Fasting blood draw: ONE 5mL pearl top tube (for BNP), TWO 3mL lavender top tubes (for CBC, HbA1C); ONE 4mL lime top tube [for uric acid, ALT, CK, Chemistry panel (electrolytes, glucose, blood urea nitrogen and creatinine)], ONE 4mL gold SST tube (for insulin), and ONE 2.7 mL “blue top” tube for whole blood NR and NAD+ levels
- 6MWT
- Record of adverse events, if any
- Study drug adherence
- Record of concomitant medications or interventions, if any
- Dispense blinded study medication:
 - 750mg PO BID or Placebo for one week
 - 1000mg PO BID or placebo for one week

6.1.4 Follow-up visit 4 (week 4)

The following procedures will be performed at the follow-up visits (Day 28±3):

- Update as needed demographic information, medical history, current medical

- treatments
- Vital signs and weight
- MNQOL score
- Fasting blood draw ONE 5mL pearl top tube (for BNP), TWO 3mL lavender top tubes (for CBC, HbA1C); ONE 4mL lime top tube [for uric acid, ALT, CK, Chemistry panel (electrolytes, glucose, blood urea nitrogen and creatinine)], ONE 4mL gold SST tube (for insulin), and ONE 2.7 mL “blue top” tube for whole blood NR and NAD+ levels
- Additional blood draw 3 hours after AM NR dose: ONE 2.7 mL “blue top” tube for whole blood peak NR and NAD+ levels
- 6MWT
- Record of adverse events, if any
- Study drug adherence
- Record of concomitant medications or interventions, if any
- Dispense blinded study medication:
 - 1000mg PO BID or Placebo

6.1.5 Follow-up telephone visit 5 (week 6)

This visit will be conducted by study staff via telephone interview. The assessments include:

- Record of concomitant medications or interventions, if any
- Record of adverse events, if any

6.1.6 Follow-up visit 6 (week 8)

The following procedures will be performed at the follow-up visits (Day 56±5):

- Update as needed demographic information, medical history, current medical treatments
- Vital signs and weight
- MNQOL score
- * Fasting blood draw: ONE 5mL pearl top tube (for BNP), TWO 3mL lavender top tubes (for CBC, HbA1C); ONE 4mL lime top tube [for uric acid, ALT, CK, Chemistry panel (electrolytes, glucose, blood urea nitrogen and creatinine)], ONE 4mL gold SST tube (for insulin),
- 6MWT
- Record of adverse events, if any
- Study drug adherence
- Record of concomitant medications or interventions, if any
- Dispense blinded study medication:
 - 1000mg PO BID or Placebo

* Fasting blood draw optional in case of safety concerns

6.1.7 Final Follow-up visit 7 (week 12)

The following procedures will be performed at the final follow-up visit (Day 84 ± 5):

- Update as needed demographic information, medical history, current medical treatments
- Vital signs and weight

- MNQOL score
- Fasting blood draw: ONE 5mL pearl top tube (for BNP), TWO 3mL lavender top tubes (for CBC, HbA1C); ONE 4mL lime top tube [for uric acid, ALT, CK, Chemistry panel (electrolytes, glucose, blood urea nitrogen and creatinine)], ONE 4mL gold SST tube (for insulin), and ONE 2.7 mL “blue top” tube for whole blood NR and NAD+ levels and FOUR 4.5 mL GLASS blue top tubes (for mitochondrial function)
- 6MWT
- Echocardiography
- Record of adverse events, if any
- Study drug adherence
- Record of concomitant medications or interventions, if any
- Record of efficacy endpoints, if any

6.1.8 End of washout telephone visit (30 days post Final Follow-up Visit)

The washout visit will be conducted by study staff via telephone interview. Washout visit assessments include:

- Record of concomitant medications or interventions, if any
- Record of adverse events, if any

7. Sources of Materials

Data will be collected throughout the study from participants on their health status and concomitant medications. Clinical, demographic and laboratory values collected as a part of the Study will be stored in a multidimensional database at the UW Clinical Atherosclerosis Research Laboratory (CARL). All lab samples are identified by a study number only. The two echocardiograms will be recorded on MOD disks during the study. Individually identifiable data is recorded in individual study charts for each participant, and in a password-protected study database. Individually identifiable data will be accessible only to the study investigators.

8. Potential Risks

Participants may experience discomfort and bruising from blood draws. Rarely, an infection could develop.

There are no known hazards to exposure of ultrasound waves, however some participants may experience discomfort at lying still.

This is a study of a nutritional supplement. For those participants taking nicotinamide riboside, a warm flushing sensation may occur when first taking this supplement. We will monitor for skin rash, increased blood sugar, or cause mildly abnormal hepatic function. In diabetic participants, it is possible that nicotinamide riboside may worsen glucose intolerance and necessitate an adjustment in medications for treatment of diabetes. We also will monitor for worsening in signs and symptoms of heart failure, by asking about worsening of dyspnea, dyspnea on exertion, orthopnea, paroxysmal nocturnal dyspnea, arrhythmia/palpitations or edema.

9. Adequate Protection Against Risk

Recruitment and Informed Consent. Recruitment for this proposed study will be conducted according to the IRB policies at the University of Washington, as well as HIPAA policies.

Potential study participants will be identified under HIPAA waiver by chart review. Their cardiologist will approve the approach before researcher contact. Potential participants will be contacted by phone using the approved phone script, or seen in person if at the clinic. Only if the participant expresses any interest will we continue study recruitment. To the participants who are interested in the study, study staff will explain the study's purpose and design and what would be required of participants. A series of questions will be asked to make sure the participant meets eligibility requirements. Then, the informed consent will be conducted by an investigator or a study coordinator. Participants will be encouraged to ask questions and to share the information with their regular doctor. A copy of this consent will be given to the participants; the original will be placed in the participant's study chart.

Protection Against Risks. All access to individually identified participant data is limited to the investigators who are directly involved in this research study, the clinical research staff of the Translational Research Unit during the subjects' visits, and the UWMC Research Testing Service. Study charts and password-protected databases are confidential and are not released to outside parties except at the participant's request. All blood samples for laboratory analysis outside UWMC are ONLY identified by a study number. The Study charts containing paper forms will be stored in the locked file cabinets in the research clinics or offices where they only can be accessed by the investigators. Each participant will receive a unique study number. The study number is linked to the participant's personally-identifiable information in the study database and used to perform data entry and linking.

Notification of Participants and Their Physicians. Study participants and their primary care or vascular care physicians will be notified if there is clinical worsening of their heart failure. We will leave the further clinical follow-up and treatment plans to be made by the participants' physicians. Participants will not be notified of the results of other laboratory studies performed specifically for this Study.

10. Potential Benefits of Research to the Participant and Others

Individual participants may benefit from this study by being on a nutritional supplement that has shown some promise in animal models of heart failure.

11. Importance of the Knowledge to be Gained

If the Study can demonstrate that nicotinamide riboside is safe and well-tolerated in participants with systolic heart failure, this will form the basis of a follow-on study to assess the efficacy of nicotinamide ribose on surrogate endpoints in heart failure, such as functional capacity and ejection fraction. Thus, the Study may provide information necessary to further explore the clinical utility of this nutritional supplement in the treatment of systolic heart failure, a large and growing population of high risk participants for whom treatment, at present, is less than adequate.

12. Data Safety Monitoring Board

A Data Safety Monitoring Board (DSMB) will be instituted for this Study in order to ensure its ongoing safety and to oversee the Interim Analyses. Recommendation for trial continuation will be guided by monitoring boundaries at interim analyses at which formal efficacy analysis is performed as well as safety evaluations at all safety data reviews. Safety review meetings will be held by the DSMB prior to Study initiation, at which time the DSMB will develop any formal "stopping rule(s)" for the Study. The DSMB will meet three

additional times: after completion of 10, 20 and 30 Study participants. Safety data will include pre-specified evaluation of parameters for blood glucose, myopathy, hepatotoxicity, renal function as well as signs/symptoms of heart failure, or other possible clinical side effects such as gout, as requested by the DSMB. Enrollment to the study will continue throughout the scheduled meetings of the DSMB. The three-member, Study DSMB Roster is provided below.

- **[name].** (Chair)
Director, Clinical Trials Service Unit and Professor of Medicine (Cardiology)
University of Washington School of Medicine
- **[name]**
Professor of Medicine and Head, Division of Cardiology
University of Washington
- **[name]**
Deputy Director, Clinical Trials Service Unit and Assistant Professor of Medicine
(Cardiology)
University of Washington School of Medicine

**NR in HF Study: Biostatistical Analysis Plan.**

**5.a. Statistical Methods.** After import into statistical software (R, Stata or SAS), data will be screened for outliers and the validity of any outlier values will be verified and/or any potential errors will be corrected. Changes in outcomes (including serum NR level, NADH/NAD+ ratio, 6MWT, MNQOL score, 3D-Echo, Doppler/TDI) from Week 0 to Week 12 will be compared between the NR and placebo arms using a two-sample t-test, the Mann-Whitney test or the permutation test, as appropriate. Changes in serum NR, NADH/NAD+ levels, 6MWT and MNQOL score outcomes over the multiple visits (0, 2, 4, 6, 8 and 12 Weeks) will be explored visually and by calculating and tabulating mean outcomes for each visit by assigned treatment.

Power calculations. Detectable differences for LVEF are calculated from power calculations for a two-sample t-test (PASS 2008, NCSS, Kaysville, UT), using the initial sample sizes of 20 patients in the NR group, 10 patients in the placebo group, and a dropout rate of 10%, leading to a final expected sample size of 18 and 9 patients in the NR and placebo groups, respectively. Two-sided tests, 0.05 significance level and 80% power are assumed. Based on these parameters we calculate a detectable difference of 1.190 standard deviations for a change in an outcome between the means in the placebo and NR groups. The standard deviation (SD) for the change in LVEF by 3D Echo is based on a study of 50 patients with LV dysfunction due to previous MI (32). The SD for change, measured between baseline and one year follow-up, was 7%, and scatterplots for the LVEF changes measured by MRI or 3D echo suggested that SD values for EF are similar for both modalities. We conservatively assumed that the SD at 12 weeks would not be smaller than that at 52 weeks.

Expected results. Assuming a 7% SD for LVEF change (32), the detectable difference by 3D-TTE for this 30 participant trial is 8.3%. Much larger sample sizes would be required to detect much lesser changes in LVEF. Thus, Study echocardiograms will explore the potential range of effect sizes for NR on LVEF.

|   |   |                   |
|---|---|-------------------|
| 
Table 1. Sample sizes to detect 5% or 3% differences in LVEF at 80%, 85% or 90% power (1:1 randomization and 2-sided <math>\alpha=0.05</math>). Total sample sizes are shown.
 | 
Sample Sizes (N) to Achieve Power of:
 |                   |
|   | 
85%
                                   | 
90%
 |
|   | 
74
   | 
86
         |
|   | 
198
  | 
232
        |

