1.3 Nicotinamide Riboside

NR is a relative of niacin, but a closer relative of nicotinamide which, unlike niacin, does not induce flushing or pruritis and has no effect on lipid levels. NR does not induce insulin resistance or dysglycemia in mouse models. Thus, NR would potentially be cheap, safe, well-tolerated and readily available. The application is in response to the program announcement of “Nutrition and Diet in the Causation, Prevention, and Management of Heart Failure” as NR has recently been approved for human use as a health supplement.

2. Study Objectives

The Study has three objectives: 1) to determine the safety and tolerability of NR in patients with clinically-stable, systolic heart failure (LVEF <40%); 2) to determine whether, at the doses employed, NR has measureable effects on whole blood NAD⁺ levels; and 3) to explore the potential range of effects of NR supplementation on heart failure surrogate endpoints.

3. Study design

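### The SAP tests echo, 6MWT and MNQOL changes without a planned NR minus placebo estimate or 95% CI, although its aim is to explore the range of effects; adding a baseline-adjusted estimate with an interval is a cheap, low-stakes improvement.

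*SAP*

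**What the plan says.** The third objective in protocol section 2 is "to explore the potential range of effects of NR supplementation on heart failure surrogate endpoints". After stating an 8.3-point detectable difference for LVEF, the SAP's Expected results paragraph concludes: "Thus, Study echocardiograms will explore the potential range of effect sizes for NR on LVEF".

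The methods named in SAP 5.a are:
- **Between arms:** changes from Week 0 to Week 12 in serum NR, the NADH/NAD+ ratio, 6MWT, MNQOL, 3D echo and Doppler/TDI "will be compared between the NR and placebo arms using a two-sample t-test, the Mann-Whitney test or the permutation test, as appropriate".
- **Over visits:** NR, NADH/NAD+, 6MWT and MNQOL are explored by plots and "by calculating and tabulating mean outcomes for each visit by assigned treatment". Echo is not in that list.

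Neither document mentions an NR minus placebo difference, a confidence interval or adjustment for baseline.

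The data for both are already collected. Protocol 6.1.2 takes MNQOL and 6MWT at Visit 2 as baseline, with "BASELINE echocardiography (TTE and TDI) This may also take place at screening if needed due to scheduling". Protocol 6.1.7 repeats all three at Week 12.

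**The concern.** Exploring a range of effect sizes is an estimation aim, but the only between-arm output planned is a hypothesis test. A test says whether zero is compatible with the data. It does not say which other differences are.

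This matters because of how the results will be used. Protocol section 11 says that if NR proves safe and well tolerated, "this will form the basis of a follow-on study to assess the efficacy of nicotinamide ribose on surrogate endpoints in heart failure". SAP Table 1 gives "Sample sizes to detect 5% or 3% differences in LVEF at 80%, 85% or 90% power", so differences of 5 and 3 points are the ones a later trial might target. Both are well below the 8.3 points this trial can detect, so a non-significant LVEF result is likely even if NR has an effect of that size. Without an interval, such a result does little to inform the next design.

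The outcomes are exploratory and the trial is a 30-person safety study, so the stakes are modest.

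**Working it through.** **Inputs from the SAP:** 18 NR and 9 placebo patients after 10% dropout; two-sided 0.05; 80% power; SD of LVEF change 7 points. **Assumed, because the documents do not give it:** the correlation ρ between baseline and Week 12 LVEF, shown as a range.

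**1. The SAP's own figures.** A two-sample t-test (noncentral t, 25 df) gives 1.190 SD, and 1.190 × 7 = 8.33 points. Both match. The legible Table 1 totals (74 and 86 for 5 points, 198 and 232 for 3 points) also reproduce with SD 7 and 1:1 allocation.

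**2. Power for the Table 1 differences.** With 18 v 9 and SD 7, power is 39% for 5 points and 17% for 3 points. So 61% and 83% of trials would be non-significant.

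**3. Unadjusted interval.** SE = 7 × √(1/18 + 1/9) = 2.86. Half-width = 2.060 × 2.86 = 5.89 points if the observed SD is exactly 7, or 5.82 averaged over the sampled SD.

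| Observed difference | p | 95% CI |
|---|---|---|
| 3 points | 0.30 | −2.9 to 8.9 |
| 5 points | 0.09 | −0.9 to 10.9 |

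**4. Baseline-adjusted interval.** With equal variances at both times, residual SD = 7 × √((1 + ρ)/2). The model has 24 df. Half-widths below use conventional standard errors and are averaged over chance baseline imbalance and the sampled SD. Detectable difference = 1.217 × residual SD.

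| ρ (assumed) | Half-width | Detectable difference |
|---|---|---|
| unadjusted | 5.82 | 8.3 |
| 0.5 | 5.15 | 7.4 |
| 0.7 | 5.50 | 7.9 |
| 0.8 | 5.65 | 8.1 |
| 0.9 | 5.80 | 8.3 |

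Break-even: √((1 + ρ)/2) = 1.190/1.217 = 0.978, so ρ ≈ 0.91. If the Week 12 SD is 10% or 25% larger than the baseline SD, break-even falls to 0.77 or 0.63. The residual SD cannot exceed the SD of change, so the worst case is 1.217 × 7 = 8.5 points, a loss of about 0.2.

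**5. Smaller SD of change.** The SAP carries a one-year SD over to 12 weeks: "We conservatively assumed that the SD at 12 weeks would not be smaller than that at 52 weeks". If the true SD is 5 or 4, 35% or 16% of trials are non-significant at 5 points, and 71% or 58% at 3 points. At SD 5 the detectable difference moves from 5.95 to 5.85 (assumed baseline SD 9) or stays at 5.95 (assumed baseline SD 12). At SD 4 it moves from 4.76 to 4.75 or 4.80. The gain is then close to nil.

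**6. Unequal spread between arms.** If the placebo residual SD is 1.5 or 2 times the NR residual SD, the conventional model interval covers about 92% or 88% in simulation. The pooled t-interval on changes does the same. HC3 standard errors bring coverage back to about 94% to 96%.

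**7. What HC3 costs in width.** With arm alone in the model, HC3 replaces 1/18 + 1/9 = 0.1667 by 1/17 + 1/8 = 0.1838. The interval widens by √(0.1838/0.1667) = 1.05, and the covariate adds a little more. Multiplying the half-widths in step 4 by 1.05 gives at least 5.4, 5.8, 5.9 and 6.1. Against the unadjusted 5.82, a narrower interval survives at ρ = 0.5, is about level at 0.7 and is lost above that.

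**The case against.** The strongest reply is that nothing here is wrong. Randomisation makes change scores an unbiased comparison. The SAP openly states the 8.3-point limit, says that smaller differences need much larger trials, and declares an exploratory purpose. A t-test is usually printed with an interval, and for 6MWT, MNQOL and the tabulated blood markers a point difference follows by subtracting the arm means. All of that stands. What remains is that the SAP does not commit to an interval for any outcome, lists no tabulated summary for echo, and permits rank or permutation tests that do not give a mean difference by default.

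A second reply is that baseline adjustment is a preference with little proven benefit. This stands in part. The LVEF gain rests on a correlation that is in neither document, and the LVEF ceiling for entry could narrow the baseline spread and shrink the gain. For 6MWT and MNQOL the documents give no SD, so no gain can be claimed.

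A third reply is that a conventional linear model is exposed to unequal spread with only 9 placebo patients. That is right, and it is why the fix uses HC3 and keeps the planned tests.

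A reader might also note that, if the true difference is 5 points, about 96% of non-significant trials have an interval that still contains 5. This is not evidence of harm. A valid 95% interval lies wholly below the truth about 2.5% of the time, so 1 − 0.025/0.61 ≈ 96% follows almost automatically.

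**Conclusion.** The point holds as a cheap improvement with low stakes. The stated aim is to explore a range of effects, and the SAP plans no output that shows one.

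The firm part is the interval: about ±5.8 LVEF points at SD 7 and 18 v 9, wide enough that the Table 1 differences of 3 and 5 points often cannot be told apart from zero. The uncertain part is the precision gain from adjustment. It is modest at best (5.1 v 5.8 at ρ = 0.5 with conventional standard errors), largely used up by HC3 at ρ of 0.7 or more, and can turn into a small loss if the correlation is high or the Week 12 spread exceeds baseline.

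A reader might infer that the planned tests are invalid, that the power calculation is wrong, or that adjustment would make the trial adequately powered. The documents support none of these: the tests are sound, 8.3 points reproduces, and no adjusted figure above brings the detectable LVEF difference near 5 points at SD 7.

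**What to change.** Keep the comparison sentence in SAP 5.a and add:

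> For echo measures, 6MWT and MNQOL, the NR minus placebo difference at Week 12 will be estimated from a linear model with arm and the baseline value (Visit 2, or screening for echo if done then), with a 95% CI based on HC3 standard errors. The planned tests on change will also be reported. For blood markers, the between-arm difference in change from the pre-treatment (screening) value will be reported with a Welch 95% CI, for those markers that are measured.

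The blood-marker wording uses screening because the protocol lists no blood draw at Visit 2. It is limited to measured markers because the visit schedules name NR and NAD+ levels, while the SAP also names the NADH/NAD+ ratio.

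Label 8.3% as the unadjusted planning figure.

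**Cost:** a few sentences, one degree of freedom and a little extra analysis, with no new data and no change in sample size. HC3 is slightly conservative when arm spreads are equal (about 96% coverage). There may be no LVEF gain, or a loss of up to about 0.2 points in detectable difference (8.5 v 8.3) with conventional standard errors, plus the HC3 widening. Welch is about 3% wider than the pooled interval when arm SDs are equal.
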